## 4. SAMPLE SELECTION / DATA SOURCES

### **Aim 1. Identify barriers to CBPC enrollment.**

*Sample.* 10 CBPC team members and 25 VNS Health Total members and FCP.

*Inclusion Criteria.* VNS Health Total member who refused CBPC in the previous year or family care partner (including if they are paid for their caregiving) of a VNS Health Total member who refused CBPC services in the previous 12 months. VNS Health Total members and FCP must also be 18 years of age or older, English speaking and receive a score of 15 or higher on the one-minute animal fluency test. We will emphasize recruitment of FCP of PLwD. Although 75% of VNS Health Total CPBC participants have a dementia diagnosis, PLWD are not the only patient group served by the plan. As such, having a dementia diagnosis is not a requirement for participation. This will also allow us to compare refusal rates among PLWD and those without dementia in exploratory analyses.

CBPC team members must be a part of the VNS Health Total community-based palliative care team.

*Exclusion Criteria.* VNS Health Total members and FCP are excluded if they are: under the age of 18; do not speak English; FCP primary relationship to VNS Health Total member is employee or paid care partner (family members who are paid for their caregiving are eligible); VNS Health Total member or family member of FCP enrolled in VNS Health Total's CBPC in the previous 12 months.

PC team members are excluded if they are not a member of the palliative care team.

### **Aim 2. Develop informational materials and processes to support CBPC team member-FCP-PLwD conversations about CPBC.**

*Sample.* 10-15 individuals from interested parties (PC team members, FCPs of PLwD, content/research experts). Most participants will be recruited from Aim 1 participants. Additional participants will be recruited as necessary.

*Inclusion Criteria.* Same for VNS Health Total members, FCP, and CBPC team members as Aim 1

*Exclusion Criteria.* Same for VNS Health Total members, FCP, and CBPC team members as Aim 1.

Research/Content experts will be identified and asked to participate based on expertise in areas of community-based palliative care, VNS Health care delivery, and/or data science.

### **Aim 3. Conduct a pre-post trial to determine the feasibility and acceptability of the materials and using them in existing clinical workflows for their impact on CBPC enrollment for PLwD and end-user satisfaction.**

*Sample.* Based on 2022 identification, eligibility, and refusal data, we anticipate 500 VNS Health Total members will be identified as eligible for CBPC during the study period (250 control, 250 intervention) and that

80 individuals will refuse CBPC during the pre-test/control period. Of these, 365 CBPC-eligible and 60 refusals are expected to be PLwD.

*Inclusion Criteria.* All VNS Health Total members who were identified as eligible for CBPC in the 6-month period prior to the introduction of the intervention (tailored informational materials about benefits of palliative care) and in the 6-month period following the introduction of the intervention.

*Exclusion Criteria.* VNS Health Total members who were not identified as potentially eligible for CBPC services by the 12-month mortality risk algorithm or who were identified by the algorithm as potentially eligible for CBPC services but determined by the clinical team to be ineligible for CBPC. At times, individuals are flagged by the algorithm as potentially eligible for CBPC, but upon further assessment by the palliative care team, it is determined that CBPC is not appropriate at this time. For example, someone may be flagged because they are over 90 years old and recently visited the emergency department. However, upon further assessment, the clinical team determines that they are highly functional and independent, their chronic conditions are well-managed, and the emergency room visit was for a minor head wound or something similar that did not greatly impact the individual's functional or health status.

## **5. PROCEDURES FOR RECRUITING STUDY SUBJECTS.**

### **Focus Groups and Interviews.**

*PC team member Recruitment.* We will recruit 10 CBPC team members from the VNS Health Total's clinical team that supports the community-based palliative care services program. We will present the project at team meetings and reach out to potential participants by email and/or phone, using VNS Health Total staff directory information. We will explain that participation in the project consists of participating in a 30-60-minute interview or focus group about their existing job and answering questions about what formats they prefer for receiving information. We will explain that participants may also participate in a 30-60-minute follow-up session to provide feedback on intervention materials developed as a result of Aim 1 focus groups and interviews. Individuals will be given the opportunity to ask questions about the project.

*Member and Family Care Partner Recruitment.* We will recruit 25 VNS Health Total members and FCP of PLWD and with other diseases from a group of about 160 individuals who were eligible for, but refused, CBPC in the previous 12 months. A VNS Health research staff member experienced in recruiting family members to research studies will contact the VNS Health Total member or FCP by their preferred contact method (e.g., phone, email, mail) to tell them about the study. We will explain that participation in the project consists of participating a 30-60-minute interview or focus group about their knowledge of palliative care, attitudes towards it, and reasons for refusing palliative care for themselves or their loved one. We will explain that participants may also participate in a 30-60-minute follow-up session to provide feedback on intervention materials developed as a result of Aim 1 focus groups and interviews. Individuals will be given the opportunity to ask questions about the project.

*Retention.* Given the one- or two-time, one or two-hour nature of participation, we do not anticipate any issues with retention of CBPC team members, VNS Health Total members, or FCP.

### **Clinical Trial.**

*PC team member Recruitment.* All of the CBPC team members who present the CBPC program to CBPC-eligible individuals and FCP will be asked to use the informational materials developed as part of this project when speaking with VNS Health Total members and FCP about the CBPC program. We will work with the CBPC leadership to identify effective ways to engage CBPC team members in the intervention while minimizing potential burden. CBPC team members who deliver the intervention (i.e., use the informational materials when explaining CBPC to eligible individuals and their FCP) will be asked to complete fidelity, feasibility, and acceptability measures (e.g., End User Satisfaction Survey) at 1, 3, and 6 months into intervention implementation.

*VNS Health Total Member Recruitment.* We plan to conduct a pilot clinical trial of integrating tailored informational materials on the benefits of community-based palliative care for eligible persons based on their individualized profile as identified by a validated 12-month mortality risk algorithm. Based on recent VNS Health Total data regarding the number of individuals identified as eligible for palliative care, we expect to run the pilot clinical trial with 500 eligible individuals over an enrollment period of 12 months. This sample of 500 individuals included in the Inclusion Enrollment Table represents all individuals expected to be identified as eligible for palliative care during the study period (250 prior to intervention implementation and 250 following intervention implementation).

All data collection from VNS Health Total members for the pilot trial will be taken from existing electronic health records and remotely collected. For the pilot trial, the study team will not interact directly with palliative care-eligible individuals, or their FCP. All outcomes for VNS Health Total members will be captured through an existing data source (the VNS Health Total electronic record) under a waiver of informed consent (see below).

*Retention.* To engage CBPC team members throughout the course of the intervention, we will present the informational materials at interdisciplinary team (IDT) and other team meetings prior to their introduction into clinical practice. We will also solicit feedback on introducing the intervention to the CBPC team members from the CBPC leadership team. Additionally, as part of the intervention development process, we will solicit feedback from CBPC team members about the best way to make the informational materials available and accessible to them. We will check in with CBPC team members monthly in order to ascertain how intervention use is progressing, troubleshooting issues, and responding to CBPC team member concerns regarding material content and or accessibility.

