**Table 1.**

Domain	Proposed measure (items)	Aims	Schedule	Participants
Demographic and Health Information	Age, sex, race, ethnicity, education level, perceived discrimination in healthcare encounters (FCP only), relationship to VNS Health Total member (FCP only), role on CBPC team (CBPC team members only), etc.	1-2	Baseline (Aim 1)	VNS Health Total members, FCP, CBPC team members, research/content experts (Aim 2 only)
	Age, sex, race, ethnicity, date of CBPC eligibility determination, date of CBPC refusal, diagnoses, triggering events	3	As extracted from electronic health record for pilot clinical trial analysis	VNS Health Total CBPC-eligible members
Knowledge of Palliative and Hospice Care	Palliative Care Knowledge Survey  additional questions on palliative care knowledge and attitudes 9/26/2025 8:41:00 PM	1-2	Baseline (Aim 1), following feedback on intervention materials (Aim 2)	VNS Health Total members, FCP
Intervention Development	Interview guides with questions about palliative care experiences, knowledge, barriers to participation in CBPC, including 5 rights framework (Aim 1); and user-centered design questions to solicit feedback on intervention materials (Aim 2)	1-2	1-time interview for Aim 1. 1-time think aloud session for Aim 2	VNS Health Total members, FCP, CBPC team members, research/content experts (Aim 2 only)
Intervention Feasibility and Acceptability	PC team member reports of use of intervention	3	1, 3, and 6 months into intervention delivery (Aim 3)	CBPC team members
	End-User Satisfaction Survey 	1, 3	Baseline (Aim 1); 1, 3, and 6 months into intervention delivery (Aim 3)	CBPC team members
Primary Endpoint	Number and rate of CBPC refusals (denominator=number of CBPC-eligible individuals)	3	As extracted from electronic health record for pilot clinical trial analysis	VNS Health Total CBPC-eligible members

**Data Collection Protocol.** Survey responses for Aims 1-3 will be collected in two ways: online or by telephone. Whenever possible, participants will be sent surveys to their preferred emails via REDCap, a password protected, HIPAA compliant data management system. Survey links will be unique to study

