**Aim 3 –email/letter recruitment (PC team members)**

Subject: Research Study

Dear [Colleague / name of participant]:

[Thank you again for participating in the interview portion of our research study at VNS Health to develop informational materials about palliative care.] We are ready to implement the materials and are reaching out to see if you are interested in continuing to help with this project.

You will be asked to participate in completing three 5–10-minute surveys to answer questions about your experience using the informational materials to tell eligible individuals and their family members about palliative care.

The study will be conducted by VNS Health and Rutgers University at VNS Health headquarters, {during IDT meetings}, by phone, by teleconference, or electronically at your convenience and will last about 15-30 minutes over three survey sessions. You will be compensated \$25 for each survey you complete. If you are interested in participating, please reply to this email, or email or call [research assistant] at [email, phone number]. A research assistant may also follow up with you by phone to ask about participation.

This study is confidential, and participation is entirely voluntary. Your decision whether or not to participate will not affect your relationship {or employment} with VNS Health or Rutgers. Your response is an invaluable part of our research and will help us better understand how to improve care for people with dementia and their families. If you have any questions or comments about this work, please call or email at [phone number] [[contact]](mailto:[contact])

Thank you for your consideration.

Sincerely,  
[name]

IRB# [IRB #]

NOTE: Language in {} will be included for CBPC team members only.

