## **9. ANALYTIC METHODS.**

### **Feasibility/Acceptability.**

We plan to conduct a pre/post pilot clinical trial to determine the feasibility and acceptability of an intervention to introduce tailored informational materials into clinician's discussions about community-based palliative care with VNS Health Total members who are eligible for the service. The informational materials will be tailored to the individual's risk profile as identified by a validated 12-month mortality risk algorithm. To establish feasibility and acceptability we will assess clinicians' and family care partners' assessments of the utility of the informational materials using the End-User Satisfaction Tool. End-User Satisfaction ratings for each concept are scored as 1 (almost never); 2 (some of the time); 3 (about half the time); 4 (most of the time); 5 (almost always). Minimum score is 12; maximum 60. Cumulative testing has produced percentile scores where a score of 54 corresponds to the 70th percentile. 57 = 80th and 59 = 90th. Short range test-retest scores for the overall score were .96 and the five subscales ranged from .80 to .95. Long range test-retest scores were .85 overall and .60 to .82 for the subscales. (Appendix). We will also assess whether and how the CBPC team members use the intervention (informational materials about palliative care) at regular intervals to assess fidelity and feasibility.

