### **Quantitative Analysis.**

For Aim 3, based on 2022 identification, eligibility, and refusal data, we anticipate 500 individuals will be identified as eligible for CBPC during the study period (250 control, 250 intervention) and that 80 individuals will refuse CBPC during the pre-test/control period. Of these, 365 CBPC-eligible and 60 refusals are expected to be PLwD.

We will use descriptive statistics to describe the sample. End-user satisfaction results will be reported as mean ratings for each item and across all items as a composite score. Results will also be reported by percentages of respondents by Likert scale level, as well as grouped by percent favorable and unfavorable. Percentage of clinicians finding the intervention to be feasible and acceptable and the proportion reporting using the informational materials will be calculated.

Additionally, we will determine the association between the intervention and reductions in refusal of CBPC among eligible individuals. We will use a pre/post design for this pilot clinical trial. For the pre-intervention measurement, we will calculate the number of palliative care services refusals among all palliative care-eligible VNS Health Total members (expected n=250) for a 6-month lookback period prior to introducing the informational materials into clinical practice. For the post-intervention measurement, after incorporating the informational materials into clinical practice, we will observe palliative care refusals prospectively for 6 months among all palliative care-eligible VNS Health Total members (expected n=250). We hypothesize that the number of refusals will decrease during the 6-month intervention period.

We assume we will see approximately 80 refusals among the 250 pre-intervention patients, for a refusal rate of  $80/250 = 0.32$  (or 32%) or  $H_0 = p_{pre} \geq p_{post}$ , where  $p_{pre}$  and  $p_{post}$  are the pre and post intervention CBPC refusal rates, respectively.

The table below show the post-intervention CBPC refusal rates we will be able to detect, for different power levels, assuming a total of 500 patients (250 pre, 250 post) a significance level  $\alpha = 0.05$ , and a pre-intervention CBPC refusal rate of 0.32.

Power	Pre-intervention CBPC refusal rate	Post-intervention CBPC refusal rate	Absolute rate reduction	Percent rate reduction
0.80	0.32	0.206	0.114	35.6%
0.85	0.32	0.199	0.121	37.8%
0.90	0.32	0.190	0.130	40.6%
0.95	0.32	0.178	0.142	44.4%

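### Section 5 sends the Aim 3 surveys only to team members who use the materials, which conflicts with Table 1 and Section 9 and leaves the use proportion without a defined denominator

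*Combined protocol and SAP*

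**What the plan says.** Five places in the combined protocol and SAP bear on who is surveyed in Aim 3 and how the answers are summarised.

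- **Section 5, Clinical Trial, PC team member Recruitment.** The request to use the materials goes to every presenter: "All of the CBPC team members who present the CBPC program to CBPC-eligible individuals and FCP will be asked to use the informational materials". The survey request that follows is narrower: "CBPC team members who deliver the intervention (i.e., use the informational materials when explaining CBPC to eligible individuals and their FCP) will be asked". What this narrower group is asked to do is "to complete fidelity, feasibility, and acceptability measures (e.g., End User Satisfaction Survey) at 1, 3, and 6 months into intervention implementation".
- **Section 3, Table 1.** One Aim 3 measure is "PC team member reports of use of intervention", and another is the End-User Satisfaction Survey. For both, the participants column names CBPC team members with no restriction to users.
- **Section 9, Feasibility/Acceptability.** "We will also assess whether and how the CBPC team members use the intervention (informational materials about palliative care) at regular intervals", with fidelity and feasibility as the stated purpose.
- **Section 9, Quantitative Analysis.** "Percentage of clinicians finding the intervention to be feasible and acceptable and the proportion reporting using the informational materials will be calculated". No denominator is given for either figure.
- **Section 5, Aim 3 invitation to PC team members.** There is no screen on use, but recipients are asked "to answer questions about your experience using the informational materials to tell eligible individuals and their family members about palliative care".

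Section 5 (Retention) adds monthly check-ins with team members on how use is going. These are not a Table 1 measure, and Section 9 plans no analysis of them.

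**The concern.** The survey rule in Section 5 selects respondents on the thing the survey is meant to measure. A presenter who never takes up the materials, perhaps because they do not fit the visit, falls outside the group asked about fidelity, feasibility and acceptability. That person is well placed to say why the materials do not fit the workflow.

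Feasibility and acceptability in existing workflows are what Aim 3 sets out to determine, so the use proportion is a main pilot result. It also helps in reading the refusal comparison. Refusals are counted over all eligible members in the post period, including those approached by a presenter who did not use the materials. Without a sound use figure, a null result could mean that the materials did not help or that they were not delivered.

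There is a practical side too. A coordinator working from Section 5 and one working from Table 1 would send the surveys to different people.

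**Working it through.** The plan states no figure for use or acceptability, so there is none to reproduce. The power table in Section 9 concerns the refusal rate and is not an input here.

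**Step 1: compare the passages.** In Section 5 the *i.e.* clause defines delivering the intervention as using the materials, so a non-user is not asked. Section 9 wants to learn *whether* team members use them, and a survey of users alone cannot answer that. Table 1 has no restriction. The three cannot all be followed.

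**Step 2: proportion ever using.** Let N be the presenters and u those who have used the materials.

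- Section 5 read literally, respondents as denominator: u/u = 100% for any u.
- All presenters as denominator: u/N.

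The documents give no number of presenters for Aim 3. I assume N = 10, borrowing the Aim 1 sample of 10 CBPC team members and supposing that all present the programme.

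| Users u (assumed) | Users only, u/u | All presenters, u/10 |
|---|---|---|
| 5 | 100% | 50% |
| 7 | 100% | 70% |
| 9 | 100% | 90% |
| 10 | 100% | 100% |

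**Step 3: acceptability.** Let a be the favourable share among users and b the share among non-users. A users-only survey returns a. The whole group gives [u·a + (N − u)·b]/N. Assume a = 80% and b between 0% and 20%; neither figure is in the documents.

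- u = 5: (4.0 + 0)/10 = 40% to (4.0 + 1.0)/10 = 50%, against 80% among users.
- u = 7: (5.6 + 0)/10 = 56% to (5.6 + 0.6)/10 = 62%, against 80%.
- u = 9: (7.2 + 0)/10 = 72% to (7.2 + 0.2)/10 = 74%, against 80%.

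**Step 4: change over time.** Suppose the group surveyed is everyone who has ever used the materials, u = 8 of 10, and s still use them at 6 months.

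- s = 6: 6/8 = 75% reported, against 6/10 = 60% of presenters.
- s = 4: 4/8 = 50% reported, against 4/10 = 40%.

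The fall among ever-users can be seen, but the level is too high by N/u = 10/8 = 1.25, because those who never started are missing.

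**The case against.** The strongest reply is that one parenthesis is being read as the whole plan. Table 1, the Aim 3 invitation, the check-ins and Section 9 all speak of team members generally. Planning a proportion reporting use presupposes that some may report none. The sentence in Section 5 also has a role-based reading: since every presenter has just been asked to use the materials, those who deliver the intervention may simply mean the presenters, as distinct from colleagues who do not present. The invitation says the materials are ready to be implemented, so it appears to go out before use can be known.

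Much of this stands. It shows that excluding non-users was probably not intended, and that the outcome depends on which passage is followed. It does not remove the conflict. The only sentence in the plan's text that qualifies who is asked to complete the measures makes use the condition. No passage says that non-users will be surveyed or how they count. A non-user could reasonably take an invitation about experience of using the materials as not meant for them.

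A reader might go further and infer that the plan would report 100% use at every time point and so hide any decline. The documents do not support that. It would require re-selecting current users at 1, 3 and 6 months, which no passage describes, and step 4 shows that following ever-users reveals a fall. The check-ins give a further, informal view of non-use.

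Two other objections are fair. Ten is the Aim 1 sample and not a stated Aim 3 team size. And placing people who never used the materials in a satisfaction denominator is debatable, because they would be rating something they had not tried. The fix allows for this.

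**Conclusion.** The point holds as an internal conflict with a missing definition. The survey group in Section 5 does not match Table 1 or the purpose stated in Section 9, and the use proportion has no denominator. Followed literally, with respondents as the denominator, Section 5 makes the ever-use figure uninformative and draws acceptability from adopters only. A later decline among ever-users would be only partly visible.

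It would be too strong to say that the plan as a whole surveys only users, or that near-100% use is built in. That result needs the literal reading, respondents as the denominator, and use understood as ever-use.

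The size cannot be fixed from the documents. It is small if nearly all presenters use the materials, though a users-only survey could not show that they do. The contrast of 100% with 50% to 90% rests on an assumed 10 presenters with 5 to 9 users, and the acceptability ranges rest on assumed favourable shares. The survey instruments are not in the text reviewed, so whether the use form allows a report of non-use could not be checked. Measurement of the primary endpoint, refusals taken from the electronic record, is not affected.

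**What to change.** **Section 5, Clinical Trial.** Send the 1-, 3- and 6-month surveys to every CBPC team member who presents CBPC during the intervention period, whether or not they used the materials. Ask about use and reasons for non-use first. Word the Aim 3 invitation so that a non-user can see it applies to them.

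**Section 9, Quantitative Analysis.** Name all presenting team members as the denominator for the use proportion at each time point, and report the response rate beside it. Report satisfaction and acceptability among users, with non-users' views on feasibility and their reasons for non-use shown separately.

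**Cost.** Short wording changes in two sections and a few more surveys. Each added person costs at most 3 × $25 = $75. With the assumed 10 presenters, 1 to 5 non-users would add $75 to 5 × $75 = $375. The reported percentages may be less favourable. The change is best made before launch, because non-users' reports at 1 and 3 months cannot be recovered reliably afterwards.
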